9.4.5.4 Exploratory Efficacy Analysis

All the analyses of the exploratory endpoints will be conducted on the ITT.

The exploratory efficacy analyses are aimed to explore the effect of the anamorelin on different endpoints but are not part of the multiplicity adjustment, thus have no confirmatory value. The exploratory efficacy endpoints are detailed in Section 3.1.3.

The duration of benefit and mean change from baseline endpoints will be analyzed like the main analysis for the primary efficacy endpoints or the analyses of the secondary endpoints.

All the changes from baseline exploratory endpoints except the HAS and the PGIS/C will be analyzed using an ANCOVA model, with explanatory variables being the randomized treatment, the stratification factors and the baseline value. Specifically, for the imputation of the 5-item Anorexia Symptom Subscale, the stratification based on the 5-IASS baseline will not be introduced in the model as the 5-IASS baseline value itself will be part of the model.

The estimator of the effect will be the difference in change from baseline between the test group and the placebo group estimated as the difference in LS means of the ANCOVA model. The least squares (LS)-mean and 95% confidence interval will be presented per treatment group together with the LS-mean placebo-corrected treatment effect and its 95% confidence interval. Statistics will be evaluated in each imputed datasets and pooled using Rubin's method.

All the responder analyses (CCR and achievement of responder threshold) will be analyzed using a logistic regression, with explanatory variables being the randomized treatment, and the stratification factors. CCR is a composite measure including both $a \ge 5\%$ body weight

gain from baseline and increase ≥ 2 points in the 5-item Anorexia Symptom Subscale score from baseline in patients who survive until the Visits of the analysis. CCR at week 9 was defined as primary efficacy endpoint in protocol version 3.0 and previous editions.

Frequency and rate of responders will be reported with 95% confidence intervals (CIs). For the treatment comparison, the odds ratio will be reported with 95% CIs. Statistics will be evaluated in each imputed datasets and pooled using Rubin's method.

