8.4. Covariates

Business & Decision

Life Sciences

The three stratification factors at randomization are used as categorical covariates in each statistical model:

- Systemic anti-cancer treatment line (first line vs second line vs third or higher line)
- Cancer treatment (immunotherapy vs no immunotherapy)
- The 5-item Anorexia Symptom Subscale (≤10 vs >10).

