8.6. Subgroups analyses

Subgroup analyses (specifically the analysis of the coprimary and secondary efficacy endpoints) will be performed for the subgroups for which numerical feasibility was confirmed at the BDRM, as defined by the following variables:

HELSINN

T AN001 Effective Date 25 JUL 2022 Approved Version 2.00

- Age (≤ 65 years or > 65 years)
- Gender
- Systemic anti-cancer treatment line (first line vs second line vs third or higher line) – stratification factor
- Cancer treatment (immunotherapy vs no immunotherapy) stratification factor
- The 5-item Anorexia Symptom Subscale (≤10 vs >10) stratification factor
- Patients who completed 24 weeks treatment

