10.1.2. Primary efficacy analyses

The primary efficacy analyses will be conducted on the ITT set. Statistical hypothesis H_{0w} and H_{0a} , as defined in Section 7.3, will be tested using an Analysis of Variance (ANOVA) model including treatment group and the three stratification factors at randomization as categorical covariates, at a Type-I error threshold of 0.05 two-sided.

As anticipated in the beginning of this Section 10, inferential analysis will be done after imputation of missing data. An established number (N=100) of imputations will be

performed and for each of the imputation the ANOVA model will estimate treatment effect and the related standard error. The pooling of the estimates will be computed using the Rubin rule (1). The pooled effect and the related p-value will be interpreted for the primary efficacy analyses. In addition, the 95% confidence interval of the pooled difference and the least squares (LS)-mean with the 95% confidence interval will be presented per treatment group.

More details for the multiple imputation process are described in Appendix 12.1.

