- ANAM and placebo patients without missing data (all assessments observed)
- ANAM and placebo patients with at least 1 missing assessment imputed by the imputation process.

Note: it is theoretically possible that aberrant values are derived because of the imputation. Aberrant values are defined as follows:

- For each item of the questionnaires:
 - a) Imputed value < the lower limit (0)
 - b) Imputed value > the upper limit (4)
- \circ For the body weight:
 - a) Imputed value < the lower limit (30 Kg)
 - b) No upper limit for the Body Weight is fixed.

In the cases (a) the imputed value will be set equal to the lower value.

In the cases (b) the imputed value will be set equal to the upper value.

Unscheduled assessments of body weight and questionnaires are not considered for imputations. These values will be listed only (and have all ANL0XFLs set to blank).

 Application of Exception 1: Apply MAR (as correction to the previous control-based imputation on patients fulfilling Exception 1) *Note: Values to be imputed with MAR need first to be re-set at missing.* A flag before starting with the imputation process should identify the cases where the exception 1 should be applied. Imputed values after MAR imputation should be within the aberrant values described above for the MNAR imputation
 According to Exception 2: Impute worst value at subject level.

A flag before starting with the imputation process should identify the cases where the exception 2 should be applied. Worst value should be calculated before any imputation.

- The imputation process does not distinguish between missing due to treatment discontinuation and death. All imputed assessments after death must be set to missing.

No covariates, apart from treatment arm (as by variable or covariate, as relevant) and baseline value will be included in the MI models.

For each variable, 100 imputed values will replace each missing value.

The following variables will be separately imputed according to the above mentioned single or multiple imputation methods:

- Weight
- 5-IASS
- 4-item Anorexia Concerns Subscale (4-IACS)
- 12-item A/CS domain

Business & Decision

Life Sciences

- FAACT total score
- FACT-G total score
- FAACT TOI
- Functional Assessment of Chronic Illness Therapy-Fatigue (FACIT-F)
- FACIT-F TOI score

The PGIS and the PGIC endpoints and the hunger assessment will not be imputed.

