12.2.1.2. MAR imputation

PROC MI DATA=DATA1 SEED=458122 OUT=DATA2B NIMPUTE=1; BY _IMPUTATION; CLASS TRTPN; VAR TRTPN W_00 W_03 W_06 W_09 W_12 W_15 W_18 W_21 W_24; MONOTONE REGRESSION; RUN;

Note: DATA2B dataset derives from DATA2A (see output dataset from MNAR placebo control-based imputation) after re-setting at missing the assessments as per Exception 1 (see above)

DATA DATAx ; SET DATAx; Where &sel; <<iidentification of the worst value (WORST) for the subject where: At least 2 non-missing: Xlast<X1 Xlast<baseline >> Run: Data Datax2; Set datax; if W 09=. then W 09=WORST; if W 12=. then W 12=WORST; if W 15=. then W 15=WORST; if W 18=. then W 18=WORST; if W 21=. then W 21=WORST; if W 24=. then W 24=WORST; RUN;

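### The imputation models omit the stratification factors that the ANOVA and the subgroup analyses use, with no reason given; the resulting bias is conditional and modest, and the remedy is cheap

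*SAP*

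**What the plan says.** **Imputation.** SAP 12.1.1.2 states: "No covariates, apart from treatment arm (as by variable or covariate, as relevant) and baseline value will be included in the MI models". The examples in SAP 12.2.1 also use the patient's own earlier visits. The MAR code in 12.2.1.2 lists "VAR TRTPN W_00 W_03 W_06 W_09 W_12 W_15 W_18 W_21 W_24", and the note in 12.2.1.1 brings in preceding visits step by step. Neither names a stratification factor. Each variable is imputed separately, so imputing weight uses no 5-IASS information.

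**Analysis.** SAP 10.1.2 tests the co-primary endpoints with an ANOVA "model including treatment group and the three stratification factors at randomization as categorical covariates", and SAP 10.2.2 applies the same model and imputation to the secondary endpoints. SAP 8.6 says "Subgroup analyses (specifically the analysis of the coprimary and secondary efficacy endpoints) will be performed", and all three factors are among the grouping variables. SAP 8.3.1 uses the same imputed datasets for every efficacy endpoint.

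**Passages that point the other way.** SAP 8.4 says: "The three stratification factors at randomization are used as categorical covariates in each statistical model". Protocol 9.4.5.4 says that "for the imputation of the 5-item Anorexia Symptom Subscale, the stratification based on the 5-IASS baseline will not be introduced in the model", because baseline 5-IASS is already there.

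**What is missing.** Protocol 9.4.1 lists no imputation covariates. SAP 7.2 reports that the power simulations varied them from many to none, but gives no ground for the final choice. SAP Section 13 does not mention it. No sensitivity analysis covers it: 10.1.3.1 only removes the exceptions to the main rule, and 10.1.3.4 corrects the strata only in the analysis model.

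**The concern.** An imputation model should normally contain at least the variables in the analysis model. If a factor is left out, patients with the same history get the same expected value whatever their stratum. Where the factor still matters given that history, values in the poorer stratum come out too high and those in the better stratum too low. These errors cancel between arms in some dropout patterns and not in others.

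Two results are exposed:

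- **The 5-IASS comparison.** It has the lower stated power (78% to 87%), and both co-primary tests must succeed.
- **The subgroup estimates.** They are split by the very factors that the imputation ignores.

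**Working it through.** **1. Inputs from the documents.** There are 158 patients per arm, alpha is 0.05 two-sided, and the 5-IASS effect is 1.2 to 1.4 points (SAP 7.2). The documents give no figure for the imputation model, no SD, no dropout rate and no stratum effect.

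**2. The plan's own figures.** The 158 per arm for CCR (7.5% vs 20%, 90% power) reproduces: the two-proportion formula gives 158, with power 90.1%. The 5-IASS power came from simulation and cannot be reproduced directly, but it implies an SD through SD = delta / [(1.96 + z_power) × √(2/158)]:
- 1.2 points at 78%: 1.2 / (2.732 × 0.1125) = 3.90
- 1.4 points at 87%: 1.4 / (3.086 × 0.1125) = 4.03

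The two agree. With SD 3.95, the standard error of the effect is 3.95 × 0.1125 = 0.44 points.

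**3. When the overall effect is biased.** A large-sample simulation (200,000 per arm, four visits, sequential regression on baseline and earlier visits, ANOVA on treatment and stratum) compared imputation with and without one binary stratum. Assumptions: SD 3.9 to 4.1, on-drug effect 1.3, and a residual stratum effect of 0, 1 or 2 points. The table shows the MAR rule with a constant residual effect of 2 points and a true effect of 1.293. The gap difference is (active, stratum 1 minus stratum 2) minus (placebo, stratum 1 minus stratum 2).

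| Dropout %, active; placebo (stratum 1/2) | Gap difference | Bias, factor omitted |
|---|---|---|
| 30/30; 30/30 | 0 | −0.004 (−0.3%) |
| 40/20; 40/20 | 0 | −0.006 (−0.4%) |
| 40/40; 20/20 | 0 | −0.006 (−0.5%) |
| 40/20; 30/30 | 20 | +0.042 (3.2%) |
| 40/20; 20/40 | 40 | +0.090 (7.0%) |
| 50/10; 10/50 | 80 | +0.182 (14.1%) |

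The bias is nil when the gap difference is zero and roughly doubles as the gap difference doubles. With residual effect 0 it is nil even for the last two patterns (−0.003 and −0.002). Reversing the dropout pattern reverses the sign. With the factor included, bias is at most 0.007 in every scenario.

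Across both rules, residual effects of 1 to 2 points and constant or growing effects, the ranges are:
- moderate pattern (gap 20): 1.5% to 5.9%
- strong pattern (gap 40): 3.4% to 12.2%
- very strong pattern (gap 80): 7% to 24.5%

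The moderate range is about 0.02 to 0.08 points (0.015 × 1.29 to 0.059 × 1.29), or 0.04 to 0.17 standard errors.

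**4. A trial-sized check under the control-based rule.** This used 400 simulated trials. Assumptions: third line is 20% of patients and 1 kg or 2 points worse; dropout per visit in that stratum is 18% on anamorelin and 8% on placebo.

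| Effect | Full data | Factor omitted | Factor included |
|---|---|---|---|
| Weight, all (kg) | 1.572 | 1.599 | 1.567 |
| Weight, third line (kg) | 1.336 | 1.469 | 1.318 |
| 5-IASS, all | 1.137 | 1.186 | 1.152 |
| 5-IASS, third line | 0.935 | 1.157 | 0.969 |

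The overall shift is 0.027 kg (1.7%) and 0.049 points (4.3%). In third line it is 0.13 kg and 0.22 points. With equal dropout the treatment differences were unbiased.

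**5. Subgroup contrasts with equal 30% dropout (large sample).**
- MAR: true effects 0.642 and 1.945 become 0.720 and 1.873. The contrast falls from 1.303 to 1.153, and 1 − 1.153/1.303 = 11.5%.
- Control-based: 0.566 and 1.715 become 0.569 and 1.719, so there is no shrinkage.

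The MAR shrinkage arises because one common treatment coefficient is imposed on both strata. A stratum main effect moves both arms equally and cannot undo it. A treatment-by-stratum term, or a separate fit in each arm, can. A further simulation of the MAR rule confirmed this.

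**The case against.** The case for leaving the SAP as it is has four parts.

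- **The protocol does not clearly require the factors.** A reader might infer that the SAP breaks a protocol rule. The only source is one sentence in the exploratory section, next to a list of ANCOVA terms. It excludes one factor for one variable, and the SAP agrees with it there. Further analysis detail is left to the SAP (Protocol Section 9). SAP 8.4 may mean analysis models only. This stands: the protocol implies, and does not prescribe.
- **Unequal dropout is not enough.** A reader might infer bias whenever dropout differs by arm within a stratum, or that missing values come from an average placebo patient. Neither holds. Dropout of 40% against 20% in every stratum gives no bias, and the regressions carry each patient's own baseline and earlier visits forward. The documents do not show that either condition for bias is met.
- **The size is small.** A shift of 0.05 points is 0.05/0.44, about 0.11 standard errors. For about 63 third-line patients the standard error is about 3.95 × √(2/31.6) = 0.99, so 0.22 points is about 0.2. Subgroup results are outside the testing hierarchy. This stands.
- **A small model may be deliberate.** The regressions learn from about 158 placebo patients, and the imputation rules were confirmed at the blinded review. That is a fair reason, but the SAP does not give it for the covariates, and four main-effect terms are not many.

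**Conclusion.** The mismatch is real, unexplained and not listed in Section 13. Bias in the overall effect needs both conditions together: a factor that predicts outcome beyond baseline and earlier visits, and an arm difference in dropout that varies between strata. Under assumed moderate values it is about 1.5% to 6% of the 5-IASS effect, with no fixed sign. The documents do not support saying that the primary estimates are biased, only that they are open to it.

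For subgroups, the MAR rule shrinks true differences by about 12% in the one scenario shown, even with equal dropout. That run applied MAR to every dropout. The SAP applies it only to patients whose values were not falling, so the shrinkage under the actual mix of rules should be smaller. Dropout rates, stratum effects and visit correlations are all assumptions. Exception 2 and the mix of rules were not simulated.

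**What to change.** - Add line of treatment and type of therapy as main effects to both the control-based and the MAR models. Add the 5-IASS stratum when imputing variables other than 5-IASS.
- Use the strata as randomised in the primary analysis. Use the corrected strata in the imputation as well as the ANOVA for the mis-stratification analysis (SAP 10.1.3.4).
- For subgroups defined by a stratification factor, either add a treatment-by-factor term to the MAR model (or fit it by arm), or state that these contrasts are attenuated.
- Reconcile SAP 8.4 with 12.1.1.2 and record the choice in Section 13. If the factors stay out, give the reason and add a sensitivity analysis that includes them.

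**Cost.** No new data are needed. The main effects add up to four terms (two for line, one for therapy, one for the 5-IASS stratum). The control-based regressions rest on about 158 placebo patients, fewer at later visits, so imputations become slightly noisier.

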10.3.1.3. Composite Clinical Response (CCR)

CCR is a composite measure defined as:

- 1.5 kg body weight gain from baseline and
- ≥ 3 points gain in the 5-item Anorexia Symptom Subscale score from baseline.

The two components of CCR are derived as follows:

- Achievement of 1.5 kg gain in body weight from baseline computed as
 - If change in body weight ≥ 1.5 kg then "Responder"; otherwise "Non-responder"
- Achievement of ≥ 3 points increase in 5 I-ASS from baseline computed as
 - If (5-IASS at Visit Baseline) ≥ 3 then "Responder"; otherwise "Non-responder"

CCR is then computed as

 If "Responder" in Achievement of ≥ 1.5 kg gain in body weight, and If "Responder" in Achievement of ≥ 3 points increase in 5-IASS, and If patient is alive then "Responder"; otherwise "Non-responder"

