10.3.2.4. Correlations and scatter plots

To explore the correlation between the weight gain and the improvement on the patient reported anorexia score, the Pearson's correlation coefficient between change from baseline in Body Weight and change from baseline in 5-item Anorexia Symptom Subscale respectively will be estimated overall and within each treatment group. Analysis will be performed at each Study Visit. Same analysis will be performed using the mean change over 12 weeks.

In addition, a scatter plot of the change from baseline of the two variables will be presented (change from baseline in Body Weight at Y-axis and change from baseline in 5-IASS at X-axis), with a display of the distribution of each single variable. The analysis will be performed at each Study Visit. Same analysis will be performed using the mean change over 12 weeks.

Correlation and Scatter plot will be performed both on observed data and after imputation.

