12.1.1.2. Imputation rules for Non-intermittent missing values (monotonic missingness)

Imputation rules for non-intermittent missing values are based on a main rule and some exceptions.

The rule and the exceptions will be applied separately for each efficacy parameter.

Main rule

All missing values will be imputed assuming MNAR, specifically by means of the control-based multiple imputation method.

Reason: Most of the patients are expected to have missing values from time of treatment stop. In addition, the patients under study are characterized by poor prognosis and the reasons for treatment discontinuation are expected to be more related to the background disease than to treatment failure. For this reason, it cannot be assumed that the values after the treatment discontinuation would follow the same trend as before discontinuation because the general conditions, with specific exceptions described below, after discontinuation get to worsen. The implementation of the control-based imputation is conservative because it assumes that the deterioration of the patient condition affects mainly the patients in the active treatment group.

Exceptions

- 1. Independent from reason for discontinuation of treatment, if:
 - at least two non-missing post-baseline assessments are available (first assessment = X_1 and last assessment = X_{last}) and,
 - X_{last} $X_1 \ge 0$ and $X_{\text{last}} \ge$ baseline,

then impute all the missing values with the MAR multiple imputation approach including randomised treatment as the covariate.

- 2. If reason for discontinuation of treatment = "Physician decision" or = "Withdrawal by subjects" and:
 - \circ at least two non-missing post-baseline assessments are available (first assessment = X1 and last assessment = X_{last}) and,
 - $\circ \quad X_{\text{last}} \text{ } X_1 \text{ < 0 and } X_{\text{last}} \text{ < baseline,}$

then impute all missing values to the worst value observed for the subject, considering only the on-treatment (post-baseline) timepoints.

Reasons:

Imputation for Exception 1

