13. CHANGES IN THE PLANNED ANALYSIS FROM STUDY PROTOCOL

The following changes from study protocol have been considered:

Efficacy Analysis

• Sensitivity Analysis:

Business & Decision

Life Sciences

- a subset of patients performed visits remotely due to COVID-19 restrictions and some important assessment (Body Weight) was collected and reported by the patients during the phone call. A sensitivity analysis not foreseen in the study protocol has been added in the SAP, by setting at missing the impacted values and managing these missing values using the Multiple Imputation process.
- as the presence of fluid retention may affect the assessment of weight, an additional sensitivity analyses (other than the one already anticipated in the protocol) will be conducted for the primary endpoint "Mean change in body weight from baseline over 12 weeks, excluding entirely patients with fluid retention observed at any point during the study.
- some cases of mis-stratifications were confirmed for a subset of patients. Thus, a sensitivity analysis has been added in the SAP to repeat the primary efficacy analysis using the correct strata information as part of the covariates included in the statistical model.
- Exploratory Analysis:
 - with the aim to better describe the clinical benefit and the responsiveness to anamorelin, a separate analysis (Changes from baseline to Week 3, 6, 9, 12, 15, 18, 21, and 24) on the most important patient-reported symptoms and functional items extracted from FAACT total score have been added:
 - Items GP1, GP7, GF5, GF6 GF7 related to physical and functional well-being
 - Items ACT1, ACT2, ACT4, ACT13 related to A/CS part
 - Items HI7, HI12, AN2, AN5, AN12 related to FACIT-F (Fatigue) questionnaire
 - the evaluation of the effect of anamorelin on Overall Survival has been incorporated into the Study Design as a safety objective to verify that no detrimental effect of anamorelin were observed. Anamorelin is not an anticancer medication, and as such, it is not expected to have a measurable positive impact on PFS or OS. The ANAM studies were not designed to detect a potential survival benefit of anamorelin mediated by body weight gain and improvement of anorexia symptoms. The relationship between changes in body weight and the 5-IASS will therefore not be analyzed, neither in the overall study population nor at

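### Weight and 5-IASS are imputed in unlinked models but paired within patients in the exploratory post-imputation correlation and, to a small extent, in the CCR; Section 13 also contradicts the planned correlation

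*SAP*

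**What the plan says.** **Imputation.** After setting out the rules, SAP 12.1.1.2 says: "The following variables will be separately imputed according to the above mentioned single or multiple imputation methods". The list that follows names weight, 5-IASS and seven other scores. On predictors it says: "No covariates, apart from treatment arm (as by variable or covariate, as relevant) and baseline value will be included in the MI models". The choice of rule is also made variable by variable: "The rule and the exceptions will be applied separately for each efficacy parameter". One patient can therefore be imputed under MAR for weight and by the control-based or worst-value rule for 5-IASS. The example MAR code in 12.2.1.2 contains the arm and a single variable's own series: "VAR TRTPN W_00 W_03 W_06 W_09 W_12 W_15 W_18 W_21 W_24".

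**Use of the imputed values.** SAP 10.3.1.3 requires a gain of 1.5 kg and a gain of 3 points in the same living patient at the same visit. SAP 10.3.2.3 analyses this CCR in each imputed dataset. For the correlation, SAP 10.3.2.4 says: "Correlation and Scatter plot will be performed both on observed data and after imputation". It is to be estimated overall and by arm, and SAP 6.1.3 lists it as two exploratory endpoints, by visit and over 12 weeks.

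**Section 13.** At the end of a paragraph about overall survival, the SAP says: "The relationship between changes in body weight and the 5-IASS will therefore not be analyzed". It adds that this applies to the whole population and to each arm.

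**The concern.** An association left out of an imputation model is not reproduced among the imputed values. Here a patient's imputed weight and imputed 5-IASS are linked only through that patient's own earlier observed values. The post-imputation correlation then mixes patients who carry the real association with patients whose association was fixed by the imputation set-up. The CCR counts joint successes, so its rates also depend on that association.

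The documents give reason to expect a positive association: Protocol 1.1 treats anorexia as a main driver of weight loss. SAP 8.2.2 expects a material amount of missing data. What is at stake is the credibility of one exploratory correlation and, slightly, the level of the CCR rates. Separately, a programmer reading Section 13 literally would drop two listed endpoints.

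**Working it through.** **1. The plan's own figure for a joint endpoint.** SAP 7.2 sized the trial on a CCR of 7.5% against 20.0%, two-sided 0.05, 90% power.
- Odds ratio: (0.20/0.80)/(0.075/0.925) = 3.083, as in Protocol 9.2.
- n per arm = [1.960·√(2·0.1375·0.8625) + 1.2816·√(0.075·0.925 + 0.20·0.80)]² / 0.125² = (0.9545 + 0.6138)²/0.015625 = 157.4, so 158.

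This reproduces and is not in dispute.

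**2. Inputs.** From the SAP: thresholds of 1.5 kg and 3 points, and a weight effect of about 1.8 kg. The 5-IASS effect is set at 1.3 points, the middle of the SAP's 1.2 to 1.4. Assumed, because the documents give no values:
- true correlation ρ from 0 to 0.5;
- 15% to 50% missing at Week 12;
- SDs of 3.0 kg and 4.5 points;
- autocorrelation φ = 0.65 per visit;
- placebo mean changes of −0.3 kg and 0.8 points;
- dropout shared by both variables and unrelated to outcome.

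**3. Closed form, independent draws, placebo arm.** For a patient last seen k visits before Week 12, the imputed pair has correlation φ^(2k)·ρ, so the multiplier of ρ is 0.4225 (k=1), 0.1785 (k=2) or 0.0754 (k=3). With 30% missing the dropout hazard is 1 − 0.7^(1/3) = 0.1121 per visit, which gives shares of 0.0884, 0.0995 and 0.1121.
- Sum over imputed patients: 0.0884·0.4225 + 0.0995·0.1785 + 0.1121·0.0754 = 0.0636.
- Among imputed patients: 0.30 × 0.0636/0.30 = 0.064.
- All patients: 0.30 × (0.70 + 0.0636) = 0.229.

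**4. Simulation of the control-based rule**, 150,000 patients per arm, joint → separate imputation at Week 12:

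| True ρ | Missing | Correlation, placebo | Correlation, anamorelin | CCR % placebo | CCR % anamorelin | Odds ratio | Risk difference (points) |
|---|---|---|---|---|---|---|---|
| 0.2 | 15% | 0.202→0.180 | 0.205→0.180 | 10.9→10.7 | 23.1→22.7 | 2.44→2.44 | 12.1→11.9 |
| 0.3 | 30% | 0.300→0.229 | 0.306→0.239 | 12.3→11.5 | 23.4→22.3 | 2.17→2.22 | 11.0→10.8 |
| 0.5 | 30% | 0.502→0.382 | 0.504→0.390 | 15.2→13.5 | 26.8→25.1 | 2.05→2.15 | 11.6→11.6 |
| 0.5 | 50% | 0.500→0.301 | 0.507→0.311 | 15.0→12.5 | 24.9→21.9 | 1.88→1.96 | 9.9→9.4 |

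At ρ = 0 the two methods agree within simulation noise. The correlation of the 12-week mean changes moves less: about 0.30 to 0.28 at ρ = 0.3 with 30% missing. Exceptions 1 and 2, score limits and deaths were not modelled.

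**5. If the draws are not independent.** SAP 12.2 says that the printed seeds are to be used, and 12.2.1.2 prints one. In the extreme case (same seed, identical missing pattern, residual draws fully shared) the imputed pair has correlation φ^(2k)·ρ + (1 − φ^(2k)). With ρ = 0.3 and 30% missing, the average multiplier is 0.0636/0.30 = 0.212. Imputed patients then have 0.064 + 0.788 = 0.852, and all patients have 0.70·0.30 + 0.30·0.852 = 0.466. The correlation rises.

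**6. Section 13 against the rest.** SAP 6.1.3 and 10.3.2.4 plan the weight/5-IASS correlation overall and by arm. Section 13 says that this relationship will not be analysed at either level. Read literally, the two cannot both hold.

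**The case against.** The strongest reply is that little depends on this.

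- Both analyses are exploratory, and SAP 10.3.2 denies them confirmatory value.
- The SAP compares arms on the CCR by odds ratio, which hardly moves because both arms shift together.
- The correlation is also run on observed data, and Protocol 9.4.5.4 planned it on all available data.
- The attenuation is partial and its size rests on assumed inputs.
- Section 13 looks like a drafting slip. Its sentence draws a consequence from a survival paragraph, and Protocol 9.4.5.4 had planned to explore relations between the endpoints and survival.

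All of this stands, and it limits the point. It does not rescue the post-imputation correlation, where the contribution of imputed patients is set by the method and not by data. Nor does it remove the literal contradiction.

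A reader might infer more than the documents support:

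- *That the CCR treatment comparison is biased.* Steps 4 and 5 concern mainly the correlation and the rate levels; in step 4 the contrast is nearly unchanged.
- *That the bias is always toward zero.* That requires independent draws, which the SAP does not guarantee.
- *That the trial's original primary endpoint is affected.* That CCR required at least 5% weight gain and at least 2 points (Protocol 9.4.5.4); the current definition is different.
- *That the sponsor deliberately cancelled the correlation.* The context points to missing words about survival.

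**Conclusion.** The point holds as a minor one. Separate imputation makes the post-imputation weight/5-IASS correlation unreliable. With independent draws and a positive true correlation it is attenuated: 0.20 to 0.18 at 15% missing, 0.30 to about 0.23 at 30%, and 0.50 to about 0.30 at 50%. With shared draws it could be inflated. With independent draws, CCR rates fall by about 0.2 to 3 points in each arm, the odds ratio rises by 0 to 0.10, and the risk difference falls by at most about 0.5 points. These sizes depend on the assumed correlation, SDs, autocorrelation and missing fraction, and on leaving out the exceptions and deaths. The co-primary and secondary tests each use one variable at a time, so this point does not touch them. The Section 13 contradiction follows from the text alone and needs no assumption.

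**What to change.** 1. Name the observed-data correlation (Protocol 9.4.5.4, all available data) as the main result.
2. Produce any post-imputation correlation, and a CCR sensitivity analysis, from a joint imputation of weight and 5-IASS. Each visit's model should contain both histories and the same-visit value of the other variable, or correlated residuals; histories alone leave out the same-visit link. Keep the per-parameter rule and exceptions, and leave the co-primary imputations unchanged.
3. Reword Section 13 to say which relationship is dropped (apparently that with survival) and that the weight/5-IASS correlation is kept.

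Cost: one extra exploratory imputation run and one corrected sentence. The joint run departs from the plan to use the same imputed datasets for every endpoint (SAP 10.3), so the sensitivity CCR may differ slightly from its separately imputed component responder rates. The SAP should say so.
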